untreated HL and its downstream effects have been a topic of active clinical research and include reduced quality of life, increased risk of falls, cognitive decline, dementia, and Alzheimer's, [2]–[5]. Despite tremendous advances in modern digital hearing aids (HAs) [6] and the potential health benefits of their use, only one in three individuals with HL owns a HA [1]. Two of the most cited reasons for low HA adoption are the lack of perceived benefit in real-world environments (e.g., noisy environments such as restaurants) and limited access due to high cost [7]–[10]. Overcoming these HA adoption hurdles has been stymied by the proprietary nature of commercial hearing aids, which make it nearly impossible for audiology researchers to understand and evaluate the innerworkings of commercial HAs in real-world conditions. Moreover, signal processing implementations across HA manufacturers can be very different for a given technology [11], [12] making it a challenge to compare across devices and prescribe the best implementation suitable for an individual listener. To circumvent these proprietary constraints, researchers often resort to laboratory simulations of HAs [13]–[16] that may be restricted to certain forms of signal processing. The drawback of this approach is the inadequate representation of the features in a commercial HA (e.g., open-ear acoustics, microphone location, etc.) that often interact with the signal processing [17]. Alternatively, to capture effects of wearable HAs, researchers may use commercial devices as a "black box" and rely on external metrics as proxies to characterize the effects of signal processing [18], [19]. Unfortunately, this approach can reduce the scientific rigor of experiments because of the inability to precisely describe and manipulate signal processing in the HA. In order to advance hearing healthcare and enable HA innovations that could improve quality and cost, thus increasing adoption of hearing aids, audiology researchers need validated open-source HA platforms that mimic commercial HAs in form and function.

The open-source speech processing platform (OSP) was developed in response to call from National Institute on Deafness and Other Communication Disorders (NIDCD) for new open-source platforms [20], [21].The OSP serves the following functions: 1) provides researchers complete control for long-term stability for experiments, 2) Researchers can configure the hearing aid processing features and investigate interactions among these features, 3) OSP provides an integrated research environment on a single platform to streamline and support an efficient research workflow. The purpose of this project is to advance the academic proofs of concepts for researcher tools successfully completed with previous R21/R33 and R01 funding into working audiology researcher tools (Aim 1), outcomes assessment tools (Aim 2) and ecological momentary assessment (EMA) tools (Aim 3 [not included in this behavioral study]) to address the need for an open-source HA with a full range of signal processing capabilities and complete researcher control.

Specific Aims pertaining to the behavioral study are 1) Refine and validate hearing research tools and advance OSP hardware/software to commercial grade (for researchers). This aim will investigate interactions among OSP parameters such as spatial processing, compression release times, noise managenment, etc. 2) Develop and

validate outcomes assessment tools to enable researchers to present acoustic stimuli and log users' responses, along with other information such as reaction time, number of stimulus repetitions to achieve reliable behavioral responses.

The study is a within-subjects design that allows for comparison of outcomes within the same participant. Experiment 1: We will compare baseline performance(unaided) and performance with the OSP (aided) for adults with hearing loss. We will measure performance in the laboratory using common clinical tests of speech understanding in noise as well as noise acceptance. We will test aided performance with different hearing aid settings. The hearing aid settings may vary with regard to compression and noise management. Statistical analyses will use a repeated measures model to control for correlation between outcomes for the same participant.

Experiment 2: To validate the capability of the OSP to assess listener outcomes, we will also compare aided speech discrimination ability in quiet and in noise for two test modes: OSP assessment tool (stimulus presentation controlled by participant & responses collected directly from the participant on the OSP) versus conventional (stimulus presentation controlled on an external program by experimenter & paper-and-pencil responses provided by participant). Statistical analyses methods will quantify agreement, correlation, and association (linear regression) between outcomes from the two test modes.

In both experiments, each participant will be presented with all the test conditions (hearing aid settings or test modes) in a laboratory setting. The order of presentation of the test conditions will be randomized and counterbalanced across participants.

2.0 Enrollment Criteria (who can be in your study and who would not be eligible to participate in your study):

Inclusion Criteria:

- >= 18 years of age; any sex

- Sensorineural hearing loss with pure-tone thresholds between 25-85 dB HL at octave frequencies between 250 and 3000 Hz

- Speak English as their primary language

- Normal or corrected-to-normal vision (<=20/50)
- Participants will be in good health (self-report)

Exclusion Criteria:

- Clinically significant unstable or progressive medical conditions

- Participants who score < 23 on the cognitive screening test (Montreal Cognitive Assessment)

- Evidence of conductive hearing loss or middle ear issues
- Significant history of otologic or neurologic disorders

- Non English-speaking or non-native English speaking

For the purposes of test validation and calibration, we may also enroll a small group (n=50) of listeners with normal hearing, defined as pure-tone thresholds of 25 dB HL or less at octave frequencies between 250 and 3000 Hz. With the exception of having normal hearing, those participants will follow the inclusion and exclusion criteria described above.

The study will not recruit special populations such as adults unable to consent/cognitively impaired, minors, prisoners, or other detained individuals.

3.0 Sample Size:

The proposed study will recruit 100 participants (based on power analysis) with bilateral symmetric sensorineural HL in the mild to severe range, over a 2-year period. Each experiment will recruit approximately 40 participants (additional 10 account for pilot testing and attrition).

Experiment 1 (Aim 1)

We assume type I error rates of 2.5% for tests of contrasts between repeated measures within individuals. We anticipate N=40 participants will suffice to detect moderate effects of d=0.5 with 80% power. Effects of this size translate to 0.71 dB points for QuickSIN and 2.6 for ANL. These are smaller than critical differences identified for QuickSIN (2.7 dB) [22] and ANL (6 dB) [23]. A smaller sample size would provide 80% power to detect larger effects (see Table A), though even if we fall short of our recruitment and data collection goals, we will still be well-powered to detect meaningful effects in Aim-1.

Table A. Sample sizes & effect sizes for Aim-1				
Sample Size	Difference (d)	QuickSIN Diff.	ANL Diff.	
30	0.59	0.82	4.12	
35	0.54	0.76	3.79	
40	0.50	0.71	3.53	

Experiment 2 (Aim 2)

We will report 95% confidence intervals for the ICC and Pearson correlations, which will have similar widths (see Table B). A sample size of N=40 would allow for narrow confidence intervals for large ICCs and correlations; and ICC \geq 0.87 or correlation >0.87 would have a 95% confidence interval width <0.15. Smaller ICCs would have larger confidence interval widths; an ICC or correlation of 0.7 would have a 95% confidence interval width of 0.33.

Table B. Pearson correlations, ICC, and corresponding confidence interval (CI) widths for Aim-2			
Correlation	Cor. Cl	ICC	
0.5	0.48	0.5	0.47
0.7	0.33	0.7	0.33
0.8	0.24	0.8	0.23
0.9	0.13	0.9	0.13

4.0 Recruitment and Screening Methods:

Recruitment process:

The proposed study will recruit 100 adults (18 years or older) over a two-year period. Participants will be primarily recruited from an existing database in the lab that has over 300 adults with hearing loss who are interested in study participation and agreed to be contacted for future research. The lab also has access to a Communication Research Registry, a confidential database for individuals interested in continuing research participation within the Northwestern School of Communication. Additional recruitment will take place through the department's audiology clinic, local audiology clinics, local community, local senior centers, and local Hearing Loss Association of America (HLAA) chapter. Recruitment methods will include flyers and brochures to the department and local audiology clinics, local senior centers, and the local HLAA chapter; advertisements in local social media boards and newspapers; flyers on bulletin boards throughout the Northwestern campus.

Screening methods:

Prior to enrollment in the study, potential participants will go through a screening process. The screening procedure will take approximately 60-80 minutes. The following tests may be conducted to verify eligibility for research inclusion:

Test	Description/Purpose	Exclusion Criteria
Case history	Written administration; questions re: onset/nature of hearing loss, hearing aid use, otologic and medical history; CEDRA questionnaire [24]	Significant history of otologic/neurologic disorders
Otoscopy	Visual examination of pinna, ear canal, and ear drum	Significant impaction of wax, active discharge; exclusion will be determined in

		conjunction with tympanometry when appropriate
Tympanometry	Test to determine middle ear status	B-type tympanogram suggesting unhealthy middle ear status
Audiogram*	Air conduction (250 Hz to 8000 Hz) and bone conduction (500 Hz to 4000 Hz) testing to determine degree and type of hearing loss	Evidence of conductive hearing loss (air- bone gap > 10 dB HL); Hearing loss > 85 dB HL at any frequency between 250-3000 Hz
Monosyllabic word recognition	Percentage of phonetically- balanced words repeated in quiet at a comfortable loudness.	Evidence of significant asymmetry between ears [25]
Montreal Cognitive Assessment (MoCA) [26]	Cognitive screening test that assesses orientation to time and place, short-term memory, and ability to follow simple commands	The scope of this study does not include cognitive impairments, therefore, we will exclude participants with a score lower than 23 [27] (suggests dementia)
Vision Screening	Screen for normal or corrected- to-normal vision using a letter/number chart	Normal/corrected-to-normal vision is required because the study involves selection of response options seen on a computer/tablet screen. MoCA (above) involves identifying/copying visual objects. We will exclude subjects who fail vision screening.

Interested participants will be contacted by the research staff via phone/email as preferred by the potential participant. At this time, the participant will be provided with basic information regarding study procedures and inclusion criteria. The lab manager will be the primary point of contact to coordinate all recruitment and scheduling, and [name] (PI) will be available as needed.

*For participants recruited from outside our lab pool or any participant who does not have a valid audiogram, we may adopt the following procedures:

- a) Request the participant to provide a copy of their existing audiogram (if available) completed by an audiologist outside of our lab. The participant will be asked to upload a copy of their hearing test via REDCap. If a participant is unable to access REDCap, they can send a copy of their hearing test via fax or to an encrypted email address.
- b) We may obtain air conduction thresholds using a validated remote automated test (e.g., GSI AMTAS Flex [28]) delivered to the participant via a tablet and calibrated headphones. The participant will be asked to complete the test in a quiet room with minimum distractions. The automated hearing test is HIPAA-compliant and FDA-registered.

Additional explanation:

All participants must be native speakers of English because our outcome measures include speech recognition of English sentences or words. Therefore,

proficiency in English is required for the validity of the results. Our study population is adults with hearing loss. Therefore, we will include individuals with sensorineural hearing loss with pure-tone thresholds between 25-85 dB HL at octave frequencies between 250 and 3000 Hz. This meets the criteria for a mild to severe hearing loss. This is the typical range of hearing loss for which individuals seek hearing aids, and the range for which hearing aids can provide sufficient gain. Participants should have no significant history of otologic or neurologic disorders as these disorders are beyond the scope of the study. The participant must have normal or corrected-to-normal vision because the cognitive screening and experiment involve visual tasks. The participants should be in general good health (based on self-report). Exclusion criteria include conductive hearing loss and middle ear issues (e.g., active discharge, significant wax impaction) as these conditions may preclude the use of a hearing aid. Participants who do not pass the cognitive screening test (< 23 on the Montreal Cognitive Assessment [26], [27]) will also be excluded because cognitive impairments may confound the results and are beyond the scope of this study.

5.0 Research Locations:

The proposed work will be conducted within the Hearing Aid Lab (Director: [name]) and in a virtual sound room (ViSoR) at Northwestern University. The lab is a 600 square foot space that includes an 8' x 8' double-walled IAC sound booth. The lab also has a meeting area with a large desk and chairs for case history-taking, cognitive assessments, and counseling, a participant waiting area with educational materials on hearing loss resources and support, and a secure file storage area. The research may also be conducted in a separate 10' X 7' sound-treated space (Frances-Searle room 1-387) that is part of the Hearing Aid Lab.

The virtual sound room (ViSoR) is within the Northwestern University Center for Audiology, Speech, Language and Learning (NUCASLL) in a building adjacent to the Hearing Aid Lab. The research staff involved in this study have access to this room.

Participant research visits may be conducted remotely. Remote participation allows a more diverse group of people to participate, especially those with limited or intermittent access to transportation, mobility challenges, or health concerns where that can be addressed by limiting in person contact, especially in light of covid 19. Remote visits may be conducted using Northwestern ITapproved (and HIPAA-approved) video conferencing or phone. The research staff will conduct these visits from a private room in their apartment and no one else will be present during the research study. The research staff may also conduct these virtual visits from the hearing aid lab or an office space. Participants will perform the remote testing from their respective places of residence/a quiet place of their convenience. The virtual visits will be conducted either through Zoom or Microsoft Teams or WebEx applications. The platform used will be determined by participant preference.

6.0 Multi-site Research (research that involves external collaborating institutions and individuals):

The current study is a behavioral research study being conducted to validate outcomes with an open-speech platform. This study is being conducted under a subaward to Northwestern University (subaward PI: [name]), and the main SBIR grant will be awarded to [name] (Nadi, LLC).

All the human subjects research work proposed here will be conducted at a single-site, i.e., at Northwestern University. Communication of results and findings will only be done with de-identified data. When sharing information, de-identified data will be exchanged via secure FTP. In addition to be being de-identified, all data will be stored in a secure password protected database or on REDcap, and will only be accessible to study staff at Northwestern University.

7.0 International Research (where data collection will occur outside the United States and U.S. territories, including online activities): NA

8.0 Procedures Involved:

Please check the boxes for all applicable data collection procedures you plan to use: \Box One-on-one interviews

□ Focus Groups

□Questionnaires/surveys

Analysis of secondary data (medical record data, educational records, government or private sector datasets, etc.)

Ethnographic observation

□ Physiological measurements (e.g., EEG, EKG, MRI)

Biospecimen collection (saliva samples, blood draws, hair samples, etc.)

□ Mobile applications/data collection devices (e.g., Fitbits, actigraphs, etc.)

Behavioral decision making tasks (e.g., puzzles, interactive games, etc.)

 \Box Physical activities such as walking and other forms of exercise

Other procedures (briefly list types of procedures here if not covered by the check-boxes above): _____

The proposed research will measure aided speech perception outcomes for hearingimpaired listeners under laboratory conditions, with a combination of hearing aid settings in quiet and noisy conditions. The study will use the OSP to provide various combinations of hearing aid signal processing. Test procedures including stimuli and outcome measures are described below.

Session	Aim 1 (Exp. 1)	Approx. Duration	Aim 2 (Exp. 2)	Approx. Duration
Session 1	Candidacy	60-80 mins	Candidacy	60-80 mins
	assessment		assessment	
	Baseline/Unaided	30 mins	Earmold	15-20 mins
	outcome		impression (if	
	measurement		needed)	
	(QuickSIN, ANL)			
	Earmold	15-20 mins		
	impression (if			
	needed)			
Session 2	Earmold + OSP	45-60 mins	Earmold + OSP	45-60 mins
	Fitting		Fitting	
	Aided Outcome	60 mins	Aided Outcome	60 mins
	measurement		measurement	
	(QuickSIN, ANL)		(MRT)	

Data collection for each experiment will include the following steps per participant:

Session 2 may take place ~7-10 days after session 1 to allow for time taken for the custom earmold order to be received.

Open-source speech processing platform (OSP):

The OSP will be used to provide amplification to the participant. The OSP mimics the functionality of a hearing aid in that it will process sound in real-time. The OSP has wearable earpieces or calibrated headphones to deliver the processed sound to the ears. However, unlike a commercial hearing aid, the processing takes places via a computer simulation of a hearing aid (portable or fixed) rather than within the housing that rests on the participants ears and also contains the microphones. The OSP allows flexible adjustments beyond what is available in commercial hearing aids, and ensures adequate scientific rigor. Different signal processing features in the hearing aid, including spatial processing and noise reduction will be varied across test conditions. Clinically realistic settings will be used. The amount of amplification with the hearing aid will be fit to a foam/ear tip or a custom earmold. These are standard clinical procedures as described below.

The OSP will be used for the duration of the experiment in a lab setting under the supervision of the experimenter. The OSP will be returned the experimenter at the end of a session.

Stimuli:

Recorded speech materials (words, sentences, or passages) will be presented. These speech materials will be combined with speech-shaped noise or multi-talker babble at varying levels (including no noise), and the intensity of the stimuli will be adjusted to represent typical conversational speech (65 dB SPL) or a comfortable level for the listener.

Earmold impression: First, the ear is visually inspected with an otoscope (lighted magnifying scope). Then a cotton/foam block and soft impression material are placed in the ear. The material is left to set for about 3 mins after which it is removed along with the cotton/foam block and is used to order an earmold for later testing. This is a standard clinical procedure.

Loudness discomfort levels: Participants will be played sounds at progressively louder levels and asked to verbally indicate the maximum point of listening comfort. Loudness discomfort levels will be measured at 0.5 and 3 kHz and used in combination with patient report. This is a standard clinical test used to verify that stimuli levels are not uncomfortably loud.

Hearing aid fitting: The ear is visually inspected using an otoscope. A small soft plastic tube is inserted into the ear canal and is used to measure the sound output of the hearing aid. The hearing aid + earmold are placed in the ear. The participant is seated in front of a speaker and sound is played from it. The sounds may be speech or noise with similar frequency content to speech, at levels ranging from soft to conversational to loud speech (50-80 dB SPL). In order to verify that the hearing aid is not uncomfortably loud, a stream of loud beeps (85-90 dB SPL) are played for 2-3 secs. Alternatively, the hearing aid fitting may be completed in a test box with a standard coupler instead of the participant's ears. These are standard clinical procedures used to adjust the hearing aid so that the programming settings are appropriate for the participant's hearing loss.

Outcome measures:

Speech recognition: The recorded speech materials that have been electronically processed and mixed with multi-talker babble or speech-shaped noise, will be presented through earphones or speakers. The speech material and noise may be presented through single or multiple speakers and from different locations in the test room. The participant will listen through the hearing aids or headphones for the duration of the experiment. The participant's task would be to either repeat the speech or select it from a list of choices on a computer monitor or provide a written response.

QuickSIN: The test measures speech recognition ability in noise. Participants will listen to and repeat recorded sentences mixed with noise. Scoring is determined by the number of words repeated correctly. Scores range from 0 to 25.5 dB SNR loss (a lower score indicates better speech recognition ability in noise). The task is expected to take 10-15 minutes for each test condition and up to 30 minutes per session. The task

duration includes time for instructions and practice. The outcome measure will be completed under experiment 1.

Modified Rhyme Test (MRT): The test is a measure of word-discrimination ability. Participants will select a word out of a choice of six rhyming words. The words may be in quiet or mixed with background noise and will be presented through the hearing aid/speakers/earphones. Participants may be asked to record their responses on paper or via button/mouse click on a computer or tablet screen. Scores will be based on percentage of words identified correctly (range: 0-100%). A higher score indicates better word-discrimination ability. Scores for phonetic-level errors and reaction times for responses may also be reported with the OSP assessment tool. The task is expected to take 30 minutes for each test condition and up to 60 minutes per session. The outcome measure will be completed under experiment 2.

Acceptable Noise Level Test (ANL): Participants will indicate the level of noise that is acceptable while listening to running speech. Scoring is determined based on the difference between the listener's most comfortable level for speech and the highest background noise level they are willing to accept. A smaller score indicates better noise acceptance. The task is expected to take 10-15 minutes for each test condition and up to 30 minutes per session. The task duration includes time for instructions and practice. The outcome measure will be completed under experiment 1.

Preference and sound quality: Sound quality and listener preferences are critical component of successful hearing aid outcomes. Multiple dimensions of sound quality may be assessed using rating scales. Participants will listen to speech or sentences that have been electronically processed, and rate each sentence for overall quality, pleasantness, clarity, noisiness, loudness, and preference. Alternatively, participants may be presented with pairs of electronically processed speech (words, sentences or paragraphs) and they may be asked to select whichever one they prefer. The speech may be presented in quiet or mixed with different levels and types of pre-recorded noise (such as multiple talkers, babble, and other environmental noise). Ratings will be provided using a graphical user interface on a tablet or computer monitor (using a touchscreen, keyboard or mouse). The task may take upto 60 minutes and may be conducted in a separate session (e.g., session 3) if needed.

The participant may be provided with a tablet or computer monitor to control (using a touchscreen, keyboard or mouse) the presentation of the stimuli via a graphical user interface. The participant will be recorded repeating the speech so that their responses may be scored later by the experimenter (also see section 15). The participant will be guided with on screen instructions and may reach the experimenter via an intercom at any time.

Acoustic measurements: After the completion of experiment by the participant, deidentified hearing aid fitting data may be retrieved from the hearing aid in order to record output on an acoustic manikin or a sound level meter within the same test conditions as the behavioral experiment. The recorded output will be used to measure signal fidelity across conditions and relate acoustic measurements with speech intelligibility. This part of the experiment does not directly involve the participant and will only be conducted with de-identified materials.

Additional procedures for remote data collection: If the participant is provided a tablet and calibrated headphones for automated audiometry, the following procedures will be used. The participant will be provided with detailed instructions on the phone or through a HIPAA-compliant video conferencing platform. The participant will be requested to complete the testing in a quiet location, with minimum distractions. In order to monitor the surrounding noise levels during the testing, the participant may be asked to record the noise levels in their room using a publicly available sound level meter application (e.g., Decibel X, NIOSH SLM). Obtaining a record of the noise level during the testing is important as high background noise may obscure the results of an audiogram.

No identifiable information will be placed on the tablet at any stage of the experiment. Completed data from each participant will be retrieved from the tablet (and erased) and housed on a secure server, before providing the tablet to the next participant.

The remote testing equipment (tablet(s) and calibrated headphones) will be provided to the participant using one of the following methods (depending on convenience):

- a) The participant may pick up the equipment from a research staff member from the curbside/parking lot by the Frances-Searle building. The participant may also return the equipment to the research staff member at the same location, upon completion of the experiment.
- b) The equipment may be delivered to and picked up from the participant's residence by a research staff member.
- c) The equipment may be mailed to the participant with a return box and shipping label.

Communication regarding the details of pickup and return of the equipment (including preferred method and date/time/location) will take place over the phone or via email. A record of the agreed upon details will be maintained by the research staff. The participant will be sent a reminder 24 hours before the scheduled time, either via email or phone (depending on the participant's preferred method of contact). A tracking number will be associated with any shipments and the package will be insured. In the event that the participant does not return the equipment by the agreed upon time/date, we will follow up with reminder emails or phone calls to determine the cause for delay and to provide them with alternative options for returning the equipment within a reasonable time frame. Participants will not be charged and financial compensation will not be withheld in the event of loss or damage to any equipment.

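### Experiment 1 tests unaided only in Session 1 and aided only in Session 2, so the unaided-versus-aided comparison cannot be separated from a session or practice effect

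*Combined protocol and SAP*

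**What the plan says.** The opening section of the combined protocol and SAP gives the first comparison of Experiment 1: "We will compare baseline performance(unaided) and performance with the OSP (aided) for adults with hearing loss". The analysis is a repeated measures model that allows for correlation within a participant. No fixed effects are listed.

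The session table in section 8.0 lists the "Baseline/Unaided" measurement of QuickSIN and ANL (30 minutes) in Session 1, with the candidacy assessment. The aided QuickSIN and ANL measurement (60 minutes) is in Session 2, with the earmold and OSP fitting. On timing: "Session 2 may take place ~7-10 days after session 1 to allow for time taken for the custom earmold order to be received". No unaided run appears in Session 2 and no aided run in Session 1. A possible third session is mentioned only for preference and sound quality.

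On order, the text before section 2.0 says "In both experiments, each participant will be presented with all the test conditions (hearing aid settings or test modes) in a laboratory setting" and then "The order of presentation of the test conditions will be randomized and counterbalanced across participants".

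For both QuickSIN and ANL, section 8.0 says "The task is expected to take 10-15 minutes for each test condition and up to 30 minutes per session" and "The task duration includes time for instructions and practice".

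**The concern.** Every participant is tested unaided first and aided at a later visit. Anything that moves the mean score between the visits enters the unaided-versus-aided difference in full. Examples are familiarity with the task, time already spent in the session (screening in one, fitting in the other) and any other systematic difference between visits. A favourable shift would be read as OSP benefit, and an unfavourable one would hide benefit. Variation from day to day that differs between participants and averages to zero adds noise, not bias. The problem is a systematic mean shift.

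The counterbalancing does not reach this contrast, because its parenthesis defines the conditions as hearing aid settings or test modes, and unaided is neither. If it were read to include unaided, it would contradict the session table.

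**Working it through.** **1. Aliasing.** Let μ be the unaided Session 1 mean, β the aided effect and s the mean change from Session 1 to Session 2.

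- Unaided runs, all in Session 1: μ
- Aided runs, all in Session 2: μ + β + s
- Aided minus unaided: β + s

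No condition is measured in both sessions, so only the sum β + s can be estimated. A session term in the model would be collinear with aided status. Two aided settings within Session 2 share the same s, which cancels, so those contrasts are unaffected.

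**2. The plan's own figure.** Section 3.0 gives N=40, type I error 2.5% per contrast, d=0.5 and 80% power. Sidedness is not stated. A paired t-test has noncentrality δ = d√N = 0.5 × √40 = 3.16, df = 39 and two-sided 2.5% critical value 2.331. Power is 79.3%. The detectable d at 80% power is 0.589, 0.541 and 0.504 for N = 30, 35 and 40, against 0.59, 0.54 and 0.50 in Table A. A two-sided 2.5% test therefore reproduces the plan. A one-sided 2.5% test gives 86.9% and does not.

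**3. Implied SD of differences.**

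- QuickSIN, Table A: 0.82/0.59 = 1.39, 0.76/0.54 = 1.41, 0.71/0.50 = 1.42. I use 1.4 dB.
- ANL: the text says "Effects of this size translate to 0.71 dB points for QuickSIN and 2.6 for ANL", which gives 2.6/0.5 = 5.2. Table A gives 3.53/0.50 = 7.06. The two disagree, so both are used.

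**4. No true benefit, favourable mean shift b (assumed).** The probability of a significant result is P(|T| > 2.331), with T noncentral t, df = 39 and δ = b√40/SD. The nominal value is 2.5%.

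| QuickSIN shift b (dB) | δ | Probability |
|---|---|---|
| 0.1 | 0.45 | 3.9% |
| 0.2 | 0.90 | 8.7% |
| 0.3 | 1.36 | 18% |
| 0.5 | 2.26 | 48% |
| 0.71 | 3.21 | 81% |

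| ANL shift b (dB) | SD 5.2 | SD 7.06 |
|---|---|---|
| 0.5 | 5% | 4% |
| 1.0 | 14% | 9% |
| 2.0 | 54% | 31% |

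**5. True QuickSIN benefit 0.71 dB, unfavourable shift u (assumed).** The net effect is 0.71 − u and δ = (0.71 − u)√40/1.4.

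| u (dB) | Net effect (dB) | Power |
|---|---|---|
| 0 | 0.71 | 81% |
| 0.1 | 0.61 | 66% |
| 0.2 | 0.51 | 50% |
| 0.3 | 0.41 | 33% |
| 0.5 | 0.21 | 9% |

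**6. Sensitivity to the SD.** Section 3.0 gives its effect sizes for within-person contrasts in general. If the unaided-versus-aided difference across visits were more variable, say 2.0 or 2.5 dB (assumed), a 0.3 dB shift would give about 9% or 7%, and a 0.5 dB shift about 24% or 15%.

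**The case against.** The case against giving this much weight has four parts.

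- **The shift is assumed.** The documents give none, and the highest probabilities need a shift of 70–100% of the effect that the study is powered for. Practice is built into both tasks, and ANL is a judgement of acceptable noise, with no correct answers to learn. This stands as a limit on size. The practice is not specified, however, and although it may shrink s it cannot make s estimable.
- **A large benefit would survive.** Section 3.0 cites critical differences of 2.7 dB for QuickSIN and 6 dB for ANL. A true benefit of 2.7 dB less a 0.5 dB shift leaves 2.2 dB, for which power is still near 100%. This stands for the significance test, though the estimate would still be off by the shift. The plan does not use the critical differences as a decision rule. It is powered for 0.71 dB and does not exempt this contrast from that target.
- **The SD may not apply to this contrast.** This stands as a caveat. Step 6 shows that a larger SD lowers the false-positive figures, but the bias in the estimate is the same.
- **Two visits may be unavoidable, and the gap is not fixed.** The 7–10 days are conditional, since impressions are taken only if needed and ear tips are allowed. That explains why aided testing waits for Session 2. It does not prevent an unaided run in Session 2, and the table fixes the unaided-first order whatever the gap.

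**Conclusion.** The concern holds. As scheduled, the unaided-versus-aided contrast in Experiment 1 is completely confounded with session. That follows from the session table and the counterbalancing text and needs no numerical assumption.

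The size of the harm is unknown. Under the plan's N, error rate and implied QuickSIN SD, a shift of 0.1 dB does little (about 4% false positives against 2.5%), while 0.3–0.5 dB gives 18–48%, or cuts power for 0.71 dB from about 81% to 33–9%. These figures rest on an assumed shift, a two-sided test and an SD carried over from the general power calculation. The finding matters for modest aided benefits and much less for large ones. It does not affect comparisons among aided settings. It should be fixed, but it does not undermine the whole study.

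**What to change.** 1. **Schedule.** Make unaided one level of the randomised, counterbalanced Session 2 sequence. Either move the Session 1 run there, or keep it as familiarisation and add one unaided QuickSIN and one unaided ANL run in Session 2. Change the parenthesis in the order statement to: *unaided and each hearing aid setting in Experiment 1; test modes in Experiment 2*.
2. **Model.** State the fixed effects for Experiment 1: condition (unaided and each aided setting) and presentation position within Session 2.
3. **Time limits.** Raise the per-session limit for QuickSIN and for ANL from 30 to 45 minutes, since 30 + 10–15 = 40–45 minutes each.
4. **Fallback.** If Session 2 cannot be lengthened, report unaided versus aided descriptively and say that it is confounded with session.

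Two optional refinements: randomise unaided to first or last place, which avoids refitting mid-sequence; and, if the Session 1 run is kept, use the difference between the two unaided runs to estimate the shift.

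**Cost.** Moving the 30-minute block takes Session 2 from 105–120 to 135–150 minutes and Session 1 from 105–130 to 75–100, with the total unchanged. The repeat option adds 20–30 minutes per participant. At the $15 per hour in section 14.0 that is $5–7.50 each: $200–300 for 40 participants, or $250–375 if the additional 10 are included, plus staff time. The downsides are more fatigue in Session 2, and removing and refitting the device when unaided falls mid-sequence.
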